8.6. Safety and Tolerability Assessments

8.6.1. Adverse Events

All AEs will be coded using the Medical Dictionary for Regulatory Activities (MedDRA) Version 22.1. All AEs will be assigned severity grade using National Cancer Institute Common Terminology Criteria for Adverse Events (CTCAE) Version 5.0.

A treatment-emergent adverse event (TEAE) will be defined as an AE that starts during or after the first dose, or starts prior to the first dose and increases in severity after the first dose.

A treatment-related TEAE will be defined as a TEAE with a relationship of related to the study treatment (LOXO-305 or Omeprazole), as determined by the investigator.

The assignment of TEAEs to the associated treatments will be as follows:

- A TEAE occurring during or after Day 1 dosing and prior to Day 8 dosing will be assigned to '200 mg LOXO-305 (Fasted)' or '200 mg LOXO-305 (Fed)' depending on the subject's fasting status prior to Day 1 dosing.

- A TEAE occurring during or after Day 8 dosing and prior to Day 15 dosing will be assigned to '200 mg LOXO-305 (Fasted)' or '200 mg LOXO-305 (Fed)' depending on the subject's fasting status prior to Day 8 dosing.
- A TEAE occurring during or after Day 15 dosing and prior to Day 18 dosing will be assigned to '40 mg Omeprazole (Fasted)'.
- A TEAE occurring during or after Day 18 dosing will be assigned to '200 mg LOXO-305 + 40 mg Omeprazole (Fasted)'.

All AEs will be listed. In addition to the data recorded in the database, the listings will include derived onset time and duration. Onset time will be calculated from the time of the last dose for TEAEs only.

The frequency of subjects with TEAEs and the number of TEAEs will be summarized for the following categories:

- TEAEs (overall, serious, and leading to discontinuation) by treatment
- TEAEs by severity and treatment
- Treatment-related TEAEs (overall, serious, and leading to discontinuation) by treatment
- Treatment-related TEAEs by severity and treatment

The frequency of subjects will be summarized separately for TEAEs and treatment-related TEAEs by the following:

- System organ class, preferred term, and treatment
- Preferred term and treatment
- System organ class, preferred term, day of onset, and treatment

For the AE data the following rules will apply:

- For the derivation of TEAE status: If the start date/time of an AE is incomplete or missing, an AE will be assumed to be a TEAE, unless the incomplete start date/time or the end date/time indicates an AE started prior to the first dose.
- For the derivation of treatment-related TEAE status: If the study treatment relationship for a TEAE is missing, a TEAE will be assumed to be a treatment-related TEAE.
- For the derivation of onset time: If the start date/time of an AE is missing, onset time will not be calculated. If the start date/time of an AE is incomplete, where possible, the minimum possible onset time will be calculated and presented in ' \geq DD:HH:MM' format (eg, if the date/time of the last dose is 01MAY2019/08:00 and recorded start date/time of an AE is 03MAY2019, then the minimum possible onset time will be calculated by assuming the AE started at the first hour and minute of 03MAY2019 [03MAY2019/00:00], thus will be presented as onset time \geq 01:16:00 in the listing).

- For the derivation of duration: If the end date/time of an AE is missing, duration will not be calculated. If the start or end date/time of an AE is incomplete, where possible, the maximum possible duration will be calculated and presented in ‘≤DD:HH:MM’ format (eg, if the start of an AE date/time is 01MAY2019/08:00 and its recorded end date/time is 03MAY2019, then the maximum possible duration will be calculated by assuming the AE ended at the last hour and minute of 03MAY2019 [03MAY2019/23:59], thus will be presented as duration ≤02:15:59 in the listing).
- For the calculation of summary statistics: If the severity of a TEAE is missing, a TEAE will be counted under the maximum severity possible, up to Grade 4 in the absence of a fatal outcome.
- For the calculation of summary statistics: If a subject experienced multiple TEAEs with the same preferred term for the same treatment, this will be counted as 1 TEAE for that treatment under the maximum severity recorded.

8.6.2. Clinical Laboratory Parameters

All clinical laboratory parameters with change from baseline, will be listed; any value outside the clinical reference range will be flagged, and whether the out of range value was deemed clinically significant or not clinically significant will be indicated. Separate listings will be provided for any parameter for which there is any individual subject value outside the respective clinical reference range.

The observed results and change from baseline for clinical chemistry, complete blood count, and coagulation parameters will be summarized descriptively by treatment group and timepoint. Boxplots of the observed values will also be provided.

Values recorded as $< x$, $\leq x$, $> x$, or $\geq x$ will be displayed in the listings as recorded. For the derivation of listing flags, calculation of summary statistics, and presentation in the figures, $< x$ and $\leq x$ values will be set to 0, whereas $> x$ and $\geq x$ values will be set to x .

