| Phosphorus | - · · · · · · · · · · · · · · · · · · · | For Female Subjects only: |
| Potassium Sodium | Urinalysis: | Pregnancy test (serum qualitative, serum quantitative |
| Total protein Triglycerides Uric acid | Bilirubin Color and appearance Glucose Ketones Leukocyte esterase | may be used for confirmation if needed) ^c Follicle-stimulating hormone (post-menopausal female subjects only) ^b Estimated creatinine clearance ^a |
| Urine Drug Screen: ^a | Nitrite Occult blood | |
| Including but not limited to the following: Alcohol (ethanol) (breath test) Amphetamines Barbiturates Benzodiazepines Cannabinoids Cocaine (metabolite) Methadone Opiates Phencyclidine Cotinine | pH and specific gravity Protein Urobilinogen Microscopic examination including bacteria, casts, crystals, epithelial cells, RBCs, and WBCs (if protein, leukocyte esterase, nitrite, or blood is positive) | |

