8.6.6. Safety and Tolerability Statistical Methodology

No inferential statistical analyses are planned.

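### SAP 8.6.2 derives out-of-range laboratory flags from substituted values (`<x` and `≤x` as 0, `>x` and `≥x` as x), which can misflag results at either end of the reference range

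*SAP*

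**What the plan says.** SAP 8.6.2 keeps the reported form of a censored laboratory result for display: it "will be displayed in the listings as recorded". For three other uses it substitutes a number. "For the derivation of listing flags, calculation of summary statistics, and presentation in the figures", results of the form `<x` and `≤x` are handled by the rule "values will be set to 0, whereas" results of the form `>x` and `≥x` follow the rule "values will be set to x". No analyte is exempted and no reason is given.

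The same section sets the flagging criterion: "any value outside the clinical reference range will be flagged, and whether the out of range value was deemed clinically significant or not clinically significant" is to be shown. It adds separate listings for any parameter that has an individual value out of range.

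The numerical summaries cover three panels: "The observed results and change from baseline for clinical chemistry, complete blood count, and coagulation parameters will be summarized descriptively by treatment group and timepoint". The section adds boxplots of the same results. Urinalysis is listed but is not among the summarised panels. On safety inference, SAP 8.6.6 says: "No inferential statistical analyses are planned".

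**The concern.** A flag answers a yes-or-no question: is this result outside the reference range? A censored result often answers it without any substitution. `<x` is certainly low if x is at or below the lower limit, and `>x` is certainly high if x is at or above the upper limit. In the remaining cases the result may not settle the question. Replacing the result by one number before the comparison can turn an unsettled case into a low flag, or a certain high into no flag.

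The treatment is also unequal. At the low end the substitute is the most extreme value possible; at the high end it is the least extreme. Zero is not a plausible value for an analyte that is always present, yet it would enter means, changes from baseline and boxplots.

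Safety and tolerability are the secondary objective and are assessed descriptively. For laboratory data, these listings, summaries and plots are the planned statistical output.

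**Working it through.** The plan states no figure here, so there is nothing to reproduce. The check is logical for the flags and arithmetical for the summaries. Write LLN and ULN for the lower and upper reference limits. The documents give no LLN, ULN or reporting limit for any analyte, so the values below are assumed, for illustration only.

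**1. Low flags.** A `<x` result becomes 0 and is flagged when 0 < LLN.

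| LLN | x | Flag after substitution | True status of `<x` |
|---|---|---|---|
| 0 | 0.1 | none | cannot be low |
| 0.2 | 0.1 | low | low |
| 0.2 | 0.2 | low | low |
| 0.2 | 0.3 | low | undetermined |

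The flag is correct in the first three rows. It can be false only when x > LLN > 0, as in the last. For `≤x` the condition is x ≥ LLN > 0, because a value exactly at the limit is in range.

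**2. High flags.** A `>x` result becomes x and is flagged when x > ULN.

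| ULN | x | Flag after substitution | True status of `>x` |
|---|---|---|---|
| 10 | 8 | none | undetermined |
| 10 | 10 | none | high |
| 10 | 12 | high | high |

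The middle row is a certain miss: the true value exceeds 10, but the substitute is exactly 10 and so is not outside the range.

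**3. Another substitute does not repair the flags.** With LLN = 0.2, `<0.2` set to x becomes 0.2 and loses a correct low flag. `<0.3` set to x/2 becomes 0.15 and is still flagged low although its status is unknown. Flags need their own rule.

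**4. Means.** If a fraction p of results is `<x`, setting them to 0 shifts the mean by −p × E[true value | true value < x]. This lies between 0 and −p·x. With 10% censored, the shift is at most 0.10x. Relative to x/2 substitution it is −p·x/2, or −0.05x in the same case.

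An illustration, assuming a lognormal analyte with a coefficient of variation of 40%:

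| Share below x | Mean, 0 used | SD multiplied by, 0 used | Mean, x/2 used | Mean, x used |
|---|---|---|---|---|
| 5% | −2.1% | 1.10 | −0.9% | +0.3% |
| 10% | −4.8% | 1.20 | −1.9% | +0.9% |
| 25% | −14.5% | 1.46 | −5.5% | +3.4% |
| 50% | −35.0% | 1.74 | −11.8% | +11.4% |

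**5. Change from baseline.** If only one of the two values is censored, the error equals the true censored value, so it is at most x. It is downward if the post-dose value is censored and upward if the baseline is.

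**6. Panels affected.** Steps 4 and 5 apply to chemistry, blood count and coagulation only. The urinalysis list in Protocol Appendix 2 includes "pH and specific gravity", for which 0 makes no sense. Since urinalysis is not summarised, only the flag logic in steps 1 and 2 applies there.

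**The case against.** The strongest reply is that little may follow in practice.

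- **Flags.** A false low needs a reporting limit above a non-zero lower limit, and nothing in the documents shows that any analyte has one. This stands. A reader might infer that the rule produces false low flags as a matter of course; the documents do not support that. Where x is at or below the lower limit, a `<x` flag is right, and where the lower limit is zero or absent, no flag arises.
- **Visibility.** The listing still shows the reported result, and clinical significance is given beside the flag. This also stands, but it does not correct the flag, and a missed high leaves no mark to prompt a second look. Whether the separate out-of-range listings are built on the derived flag is not stated.
- **Subject safety.** Protocol Appendix 4 has laboratory results available to the investigator before release from the unit, and Appendix 1 makes a laboratory abnormality an adverse event on the investigator's judgement. No document makes the SAP flag drive either. A reader might infer a risk to subject management; the text gives no basis for it.
- **Impossible values.** A reader might take a pH or specific gravity of 0 as evidence that impossible numbers enter the means. They do not: urinalysis is outside the summarised panels, and its listed values stay as reported.
- **Convention.** Zero, x/2 and x are all crude single-value choices, and SAP 8.5.2.1 also uses zero for unquantifiable drug concentrations in summaries. For summaries this largely stands. It does not defend the flags, since no reference-range flag depends on the concentration rule.

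**Conclusion.** The point holds in a conditional form and is minor. Followed as written, the rule misses a true high when a result is `>x` with x equal to the upper limit. It can also raise a false low when x lies above a non-zero lower limit (or, for `≤x`, at or above it). How many analytes meet these conditions cannot be found from the documents; the number is probably small.

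For the three summarised panels, the downward direction of the mean is certain whenever a `<x` result has a true value above 0. Its size is bounded by p·x, but p is unknown. A reader might carry away the largest illustrative figure, a mean about a third too low; that needs half of an analyte's results to be below the reporting limit, and nothing in the documents suggests such a share. At 5% to 10% censored, the same assumed distribution gives a loss of 2.1% to 4.8%.

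The consequence is confined to descriptive safety listings, tables and plots. The pharmacokinetic comparisons do not use these values.

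**What to change.** In SAP 8.6.2, separate the flag rule from the summary rule.

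- **Flags and the separate out-of-range listings:** compare the result as reported with the reference range. Flag low for `<x` with x at or below the lower limit, or `≤x` with x below it. Flag high for `>x` with x at or above the upper limit, or `≥x` with x above it. Otherwise raise no flag, and mark the status as indeterminate where the censored interval straddles a limit.
- **Summaries and figures:** use the reporting limit x (or x/2 for `<x`) in place of 0, apply the choice consistently, and footnote it. This part is a convention and remains an approximation: in the illustration x/2 biases the mean down and x biases it up.

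The cost is one or two SAP sentences and a small programming change. No additional data are needed beyond the reported results and the reference ranges already required for flagging.

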8.6.3. Vital Signs Parameters

All vital signs parameters with changes from baseline will be listed; any value outside the clinical reference range will be flagged, and whether the out of range value was deemed clinically significant or not clinically significant will be indicated.

The observed results and change from baseline for all vital signs parameters will be summarized descriptively by treatment group and timepoint. Boxplots of the observed values will also be provided.

8.6.4. 12-lead Electrocardiogram Parameters

All 12-lead ECG parameters with changes from baseline will be listed; any value outside the clinical reference range will be flagged, and whether the out of range value was deemed clinically significant or not clinically significant will be indicated.

The observed results and change from baseline for all 12-lead ECG parameters will be summarized descriptively by treatment group and timepoint. Boxplots of the observed values

will also be provided. QTcF values that are > 450 msec and increase from baseline > 30 msec will be flagged in the data listing.

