4.4. Exclusion Criteria

The following will exclude potential subjects from the study:

- 1. History or presence of any of the following, deemed clinically significant by the Investigator (or designee), and/or Sponsor:
 - i. liver disease
 - ii. pancreatitis

- iii. peptic ulcer disease
- iv. intestinal malabsorption
- v. gastric reduction surgery
- vi. history or presence of clinically significant cardiovascular disease:
- vii. Myocardial infarction or cerebrovascular thromboembolism within 6 months prior to the first dose administration (Day 1)
- viii. Symptomatic angina pectoris within 6 months prior to the first dose administration (Day 1)
- ix. New York Heart Association Class ≥ 2 congestive heart failure within 6 months prior to the first dose administration (Day 1)
- x. Congenital prolonged QT syndrome
- xi. Ventricular pre-excitation syndrome (Wolff-Parkinson White syndrome)
- xii. Arrhythmia (excluding benign sinus arrhythmia) or history of arrhythmia requiring medical intervention
- xiii. Ventricular dysfunction or risk factors for Torsades de Pointes (eg, heart failure, cardiomyopathy, family history of Long QT Syndrome)
- xiv. Significant screening ECG abnormalities:
 - 1. left bundle-branch block
 - 2. second-degree atrioventricular (AV) block, type 2, or third-degree AV block
 - 3. QT interval corrected for heart rate using Fridericia's method (QTcF) is > 450 msec
- 2. Subjects with out-of-range, at-rest (ie, supine for at least 5 minutes) vital signs at Screening, Check-in (Day -1), or prior to dosing on Day 1, including:
 - i. oral body temperature > 37.5°C;
 - ii. pulse rate < 50 or > 99 beats per minute (bpm);
 - iii. systolic BP < 89 or > 139 mmHg;
 - iv. diastolic BP < 50 or > 89 mmHg.

For these parameters, out-of-range values that are not clinically significant (as determined by the Investigator or designee) may be repeated twice during Screening, Check-in (Day -1), and predose on Day 1. Note: Rechecks of pulse rate and BP values will be permitted up to 2 times to confirm eligibility for study participation. Subjects may be eligible for participation in the study based on rechecked pulse rate and/or BP values if the values fall within the ranges stated above.

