7.2.1. Adverse Events

Adverse event definitions; assignment of severity, causality, action taken, and outcome; and procedures for reporting SAEs are detailed in Appendix 1.

Subjects will be asked a non-leading HDYF? question such as "Have there been any changes in your health status since Screening/since you were last asked?" at the timepoints specified in Appendix 4 (ie, at Screening [after the ICF is signed], at Check-in [Day -1], at each postdose vital signs assessment, and at an appropriate time for all other days). Subjects will also be encouraged to voluntarily report AEs occurring at any other time through the EOS.

Adverse events, whether volunteered, identified by the subject's responses to HDYF? inquiries, or noted on physical examination, ECG, vital signs assessments, or laboratory tests, will be recorded throughout the study (ie, from signing of the ICF until EOS [or ET if the subject discontinues from the study and does not complete a follow-up phone call]), either as subject medical history (if the event is reported as beginning prior to signing of the ICF or if the event occurs prior to study drug administration on Day 1 and is assessed as not related to study procedures by the Investigator [or designee]) or as AEs (if the event occurs after signing of the ICF but prior to study drug administration on Day 1 and is assessed as related to study procedures by the Investigator [or designee], or if the event occurs after study drug administration on Day 1 and is assessed as related to study procedures by the Investigator [or designee], or if the event occurs after study drug administration on Day 1 through EOT or ET regardless of relationship to study drug). From EOT or ET through EOS, only AEs assessed as related to study drug by the Investigator (or designee) are to be reported. All SAEs that develop from the time of ICF signing until EOS (or ET, if the subject discontinues from the study and does not complete a follow-up phone call) are to be reported.

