| | | | | | | | | | | | | | S | tudy | v Daj | ys | | | | | | | | | | | Clinic Discharge/ EOT (Day 25) or ET ^v | Follow -up Phone Call (EOS) |
|--|----------------------------------|---|---|---|---|---|---|---|---|---|---|----|----|------|-------|----|----|----|----|----|----|----|----|----|----|----|---|---|
| Study Procedures ^a | Screening (Days -29 to -2) | | | 2 | 3 | 4 | 5 | 6 | 7 | 8 | 9 | 10 | 11 | 12 | 13 | 14 | 15 | 16 | 17 | 18 | 19 | 20 | 21 | 22 | 23 | 24 | | 7 (±2) days post EOT or ET ^w |
| Prior and Concomitant Medications ^s | X | Х | Х | X | Х | X | X | X | Х | Х | Х | X | Х | X | Х | X | X | X | X | X | X | Х | X | X | X | X | Х | Х |
| Serum Pregnancy Test ^t | Х | Х | | | | | | | | | | | | | | | | | | | | | | | | | Х | |
| FSH Test ^u TSH Test | X X | | | | | | | | | | | | | | | | | | | | | | | | | | | |

Abbreviations: AE = adverse event; BMI = body mass index; BP = blood pressure; CBC = complete blood count; CK = creatine kinase; CRU = Clinical Research Unit;

ECG = electrocardiogram; EOS = End of Study; EOT = End of Treatment; ET = Early Termination; FSH = follicle-stimulating hormone; HbA1c = hemoglobin A1c; HDYF? = How Do You Feel?; HIV = human immunodeficiency virus; ICF = Informed Consent Form; PK = pharmacokinetic; SAE = serious adverse event; TSH = thyroid-stimulating hormone; UA = urinalysis.a. For details on study procedures, see Section 7.

b. Interim medical history only.

c. Weight and BMI (based on Screening height) only.

d. A complete physical examination will be performed at Screening. An abbreviated physical examination will be performed at Check-in (Day -1) and at EOT (Day 25).

- e. 12-lead ECGs will be collected after the subject has rested in the supine position for at least 10 minutes, and will be obtained prior to and as close as possible to the scheduled blood draws at Screening and Day -1, Day 1 (predose and 2 hours after LOXO-305 dosing), Day 4 (ie, 72 hours after LOXO-305 dosing on Day 1), Day 8 (predose), Day 11 (ie, 72 hours after LOXO-305 dosing on Day 8), Day 15 (predose), Day 18 (predose), Day 21 (ie, 72 hours after LOXO-305 dosing on Day 18), and at EOT/Day 25 (168 hours after LOXO-305 dosing on Day 18) or ET.

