- v. EOT is defined as when the subject is released from the CRU following completion of all assessments through Day 25. ET is defined as when the subject is released from the CRU if the subject terminates the study early. Vital signs, ECG, and safety laboratory results for clinical chemistry, hematology, coagulation, and UA are to be available for review by the Investigator or designee prior to subject release from the CRU at the EOT or ET visit.
- w. To be performed 7 days (± 2 days) following EOT or ET. EOS is defined as when the CRU contacts the subject by a follow-up phone call 7 days (± 2 days) after the EOT visit or ET visit to determine if any SAE or study drug-related AE has occurred since the EOT or ET visit. All subjects who received LOXO-305 (including subjects who are terminated early) will be contacted.

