1. INTRODUCTION

This SAP has been developed after review of the clinical study protocol (Final Version 2.0 dated 29 January 2020) and electronic case report form.

This SAP describes the planned analysis of the pharmacokinetic (PK), and safety and tolerability data from this study. A detailed description of the planned TFLs to be presented in the clinical study report (CSR) is provided in the accompanying TFL shells document.

In general, the analyses are based on information from the protocol, unless they have been modified by agreement with Loxo Oncology, Inc. A limited amount of information about this study (eg, objectives, study design) is given to help the reader's interpretation. This SAP must be finalized prior to the lock of the clinical database for this study. When the SAP and TFL shells are approved, they will serve as the template for this study's CSR.

This SAP supersedes any statistical considerations identified in the protocol; where considerations are substantially different, they will be so identified. If additional analyses are required to supplement the planned analyses described in this SAP, they may be performed and will be identified accordingly in the CSR. Any substantial deviations from this SAP will be agreed with Loxo Oncology, Inc. and identified in the CSR.

This SAP is written with consideration of the recommendations outlined in the International Conference on Harmonisation (ICH) E9 guideline *Statistical Principles for Clinical Trials* and ICH E3 guideline *Structure and Content of Clinical Study Reports*.^{1,2}

The document history is presented in [Appendix 1](#).

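### Does joining the two QTcF conditions with 'and' in SAP 8.6.4 leave notable QTcF records unmarked in a way that matters?

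*SAP*

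**What the plan says.** The QTcF-specific rule is a single sentence in SAP 8.6.4: "QTcF values that are > 450 msec and increase from baseline > 30 msec will be flagged in the data listing". The visible text does not say whether this is one flag or two.

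The same section also provides:

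- a full listing with a general flag: "All 12-lead ECG parameters with changes from baseline will be listed; any value outside the clinical reference range will be flagged". The range limits are not given. The listing also shows whether an out-of-range value was judged clinically significant;
- summaries: "The observed results and change from baseline for all 12-lead ECG parameters will be summarized descriptively by treatment group and timepoint", with boxplots of observed values.

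SAP 8.1.3 defines baseline as the last value before LOXO-305 in each period, and change as the later value minus that baseline. SAP 1 leaves output detail to a companion document: "A detailed description of the planned TFLs to be presented in the clinical study report (CSR) is provided in the accompanying TFL shells document". SAP 8.6.6 plans no inferential safety analysis.

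In the protocol, section 7.2.1 brings events "noted on physical examination, ECG, vital signs assessments, or laboratory tests, will be recorded throughout the study". Appendix 4, footnote v, requires that results including ECGs "are to be available for review by the Investigator or designee prior to subject release from the CRU". Section 4.4 lists, among significant screening ECG abnormalities, that "QT interval corrected for heart rate using Fridericia's method (QTcF) is > 450 msec".

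**The concern.** A high absolute QTcF and a large rise from baseline are two different signals, and either can be of interest alone. A rule that requires both passes over a large rise from a low baseline, and a value above 450 msec reached by a modest rise from a high baseline. The protocol's own screening criterion treats a value above 450 msec as notable without any condition on change, which makes a joint postdose rule look odd beside it.

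The wording is also open to a second reading as two flags, so two programmers could mark different rows. Safety is the secondary objective and rests on descriptive summaries and listings. A reader who scanned only the marked rows could miss a subject with a notable record. The general ECG flag does not fully close the gap, because it acts on the value and not on the size of a rise.

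**Working it through.** **Inputs.** The thresholds of 450 msec and 30 msec come from SAP 8.6.4. Baseline B and change v − B, where v is the postdose value, come from SAP 8.1.3. There is no plan figure to reproduce. The baselines below are illustrative.

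**Rules.**

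- One joint flag: v > 450 and v − B > 30, that is, v > max(450, B + 30).
- Two separate flags: v > 450 or v − B > 30, that is, v > min(450, B + 30).

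**Single records.**

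| B to v (msec) | Rise | v > 450 | Rise > 30 | Joint flag | At least one separate flag |
|---|---|---|---|---|---|
| 385 to 445 | +60 | no | yes | no | yes |
| 440 to 455 | +15 | yes | no | no | yes |
| 425 to 455 | +30 | yes | no | no | yes |
| 415 to 460 | +45 | yes | yes | yes | yes |
| 420 to 451 | +31 | yes | yes | yes | yes |

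**Where the readings differ, in whole msec.**

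| B | Joint flag above | Separate flags above | Values on which they differ |
|---|---|---|---|
| 385 | max(450, 415) = 450 | 415 | 416 to 450 (+31 to +65) |
| 400 | max(450, 430) = 450 | 430 | 431 to 450 (+31 to +50) |
| 420 | max(450, 450) = 450 | 450 | none |
| 440 | max(450, 470) = 470 | 450 | 451 to 470 (+11 to +30) |
| 450 | max(450, 480) = 480 | 450 | 451 to 480 (+1 to +30) |

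Below a baseline of 420 the joint rule passes over some rises above 30 msec. Above 420 it passes over some values above 450 msec. A baseline of 450 is not a ceiling, because the protocol limit applies at screening while the SAP's baseline is taken before the dose in each period.

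**What the plan still shows for the two main examples, followed as written.**

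| Output | 385 to 445 (+60) | 440 to 455 (+15) |
|---|---|---|
| Listing row with value and change | yes | yes |
| General out-of-range flag | only if the upper limit is below 445 | if the upper limit is below 455 |
| Change summary by treatment and timepoint | included; the maximum if largest in its cell | included |
| Adverse event recording if noted as an event | yes | yes |

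SAP 8.1.1 keeps the minimum and maximum even when fewer than three values are available, so extremes are part of the standard summary. SAP Appendix 1 records that Version 2.0 reworded 8.6.2 to 8.6.4 so that the summary tables clearly include changes from baseline.

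The listing is also short. Protocol Appendix 4, footnote e, begins the dosing-day schedule with "Day 1 (predose and 2 hours after LOXO-305 dosing), Day 4 (ie, 72 hours after LOXO-305 dosing on Day 1), Day 8 (predose", and continues with Day 11, Day 15 predose, Day 18 predose, Day 21 and Day 25. The ECGs it times by hours after a LOXO-305 dose are Day 1 at 2 hours and Days 4, 11, 21 and 25, so five per subject.

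**What depends on the flag.** Nothing in either document does. No categorical QTcF table, stopping rule, population definition or test refers to it.

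**The case for a change.** The best argument for rewording is that it costs almost nothing. One sentence split in two would keep both thresholds and remove the doubt. Summaries by treatment and timepoint do not identify the subject behind an outlying value, and helping a reader find that record is what a listing flag is for. That is true, and the sentence could be clearer.

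A second argument concerns early-termination, unscheduled and postdose repeat ECGs. SAP 8.1.2 keeps these out of all calculations except baseline derivation, and SAP 8.1 counts change from baseline as a calculation. Taken literally, such a record has no computed change, so a joint flag could not be evaluated however high the value; a separate value flag could be. These records are also absent from the summaries. This is the firmest part of the objection, but it is narrow. SAP 8.1 still requires all captured data to be listed, and the general out-of-range flag works on the value alone. Separate flags would not restore the missing change either.

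Neither argument shows that a result or a safety conclusion would differ. If the joint rule was intended, it can be programmed as it stands, and no other passage contradicts it; wanting two flags is then a preference. If two flags were intended, the sentence is a slip of wording that whoever specifies the listing can resolve.

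**Conclusion.** The logic of the concern is right: on the literal reading a QTcF is marked only above max(450, baseline + 30), and both main examples go without a QTcF-specific flag. The consequence is confined to marks in one data listing. The same values and changes appear under either reading, the summaries of scheduled assessments are identical, adverse event recording and ECG review do not use the flag, and no pharmacokinetic analysis is touched. This is a loose sentence about listing format that analysts can settle when they specify the output, so no change to the plan is called for.

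Two assumptions limit the conclusion. The shells are not available, so whether they already define the flag is unknown. The reference range limits and the QTcF distribution are not given either, so it cannot be said how many records would be marked differently, or how many of those above 450 msec the general flag already covers. Neither matters to the verdict unless some output or decision outside the visible documents relies on the flag.
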